### 4. Methods

We conducted a randomized trial to analyze the effectiveness of a personalized prescribing portrait in the primary care setting in the province of British Columbia between September 2021 and March 2022.

Physicians are randomized to three groups:

	Arm A ~33%	Arm B ~33%	Arm C ~33%
Initial mailing Sept 23, 2021	Early Portrait + Letter	Nothing	Early Letter Only
Delayed mailing Mar 28, 2022		Delayed Portrait + Letter	Delayed Portrait + Letter

\*Approximately 1,691 physicians were randomized to each group. However, not all will receive materials due to opt-outs and incorrect addresses.

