#### Study Dates:

- Early mailing (groups A and C): 23-Sept-2021
- Delayed mailing (groups B and C): 28-Mar-2022
- Letter & Portrait topic released publicly on website: 28-Mar-2022

**Study Period:** September 24th, 2021 to March 28, 2022.

**Delay Period:** March 29, 2022 to Sept 28, 2022

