#### Study Comparisons:

[figure not shown]
There will be four comparisons:

During the study period (Sept 23, 2021 to Mar 28, 2022):

- Arm A vs Arm B (impact of L+P combined)
- Arm A vs Arm C (The added impact of P in physicians who received L)
- Arm C vs Arm B (Impact of L)

During the study period (Sept 23, 2021 to Sept 28, 2022):

- Arm B vs Arm C (repeated messaging)

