## Data sources

B.C. Ministry of Health *Healthideas* data warehouse, including: ClaimsHist, MSP fee-for-service, hospital discharge abstracts, client roster, physician roster.

Estimated number of records/charts to be examined: 1691 physicians randomized to each group = 5,073. Estimate 6 UTI treated visits per physician = **30,438 patient records** to be included in the analysis.

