## 5. Statistical Analysis Plan

1. **Baseline Characteristics:** Physicians and Patients by Study Group. Age (mean, sd), age groups, sex, urban vs rural.
2. **Trends:** Weekly prescribing line chart by randomized physician group of Nitrofurantoin, Ciprofloxacin, and TMP-SMX, from 6 months prior to first mailing to the end of the delay period - 6 months after the delayed mailing (September 2022). This will illustrate background trends in prescribing patterns.
3. **Relative Risk:** Prescribing in the early and delayed intervention groups will be compared 6 months pre/post intervention. A 4-way comparison of numerators during the pre/post periods between the early and delay groups will provide an odds ratio that approximates the relative risk.xiv,xv Do this for each of the four study comparisons listed in Section 4.

Acute cystitis episodes = n

Outcome Measures	Expected Change	Intervention Physicians				Delayed Control Physicians				Crude OR	Adjusted OR	95% CL
		Time Period		Time Period		Time Period		Time Period				
		Pre		Post		Pre		Post				
		YES	NO	YES	NO	YES	NO	YES	NO			
Nitrofurantoin	+	a	b	c	d	e	f	g	h			
Ciprofloxacin	-											
TMP_SMX	-											
Other	-											
No Treatment	n/c											

$$\text{Crude OR} = \frac{(c * h)}{(g * d)}$$

Evaluation is a 4-way comparison: the ratio of change in the early group between pre and post intervention is compared to the same ratio of change in the delayed group.

$$\text{Adjusted OR} = \frac{\text{Crude OR}}{\frac{(a * f)}{(e * b)}}$$

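### The Adjusted OR subtracts the baseline difference with a coefficient fixed at 1, which costs precision in the three early-mailing comparisons against estimating that coefficient from the same data

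*Combined protocol and SAP*

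**What the plan says.** Section 4 (Methods) states that "Physicians are randomized to three groups", and its study dates give "Early mailing (groups A and C): 23-Sept-2021". Section 5, item 3 (Relative Risk) lays out an eight-cell table of episodes, with and without each treatment, before and after the intervention in two groups. The Crude OR is the post-period odds ratio, (c·h)/(g·d). The Adjusted OR is the Crude OR divided by the pre-period odds ratio, (a·f)/(e·b). In words, "the ratio of change in the early group between pre and post intervention is compared to the same ratio of change" in the delayed group. This is to be done for all four study comparisons with 6-month windows.

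Both ORs are tabulated and neither is named as primary, but the sentence "Evaluation is a 4-way comparison" points to the Adjusted OR. The plan contains no regression and no estimated baseline coefficient. It gives no ICC, no pre/post correlation and no method for the 95% limits.

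**The concern.** Dividing by the pre-period OR is a difference-in-differences on the log-odds scale. That design is needed when groups may differ systematically at baseline. Here they are randomised, so for the three early-mailing comparisons the expected log pre-period OR is zero. The pre-period data can then only reduce noise, and they do so best when weighted by how well they predict the post-period. With a handful of largely different patients per physician in each window, that prediction is far from one-for-one. A fixed coefficient of 1 therefore carries baseline sampling noise into the estimate.

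Precision matters most for the contrasts that isolate one component: the portrait added to the letter (A vs C) and the letter alone (C vs B). Their effects may be small, and the hypothesis in Section 2 makes a separate claim for each component.

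Arm B vs Arm C is a different case. If its pre-period is the 6 months before 28 March 2022, Arm C has already had the letter, and the baseline difference is no longer chance alone.

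**Working it through.** **The plan's own figures.** 1,691 × 3 = 5,073 physicians, and 5,073 × 6 = 30,438 records. Both reproduce. The 6 comes from "Estimate 6 UTI treated visits per physician" under Data sources. No period is attached to it, so m = 3, 6 and 12 episodes per period were tried.

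**The estimator.** log(Adjusted OR) = [log(c/d) − log(g/h)] − 1 × [log(a/b) − log(e/f)]. The second bracket is the log pre-period OR.

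**Variances.** Let V be the variance of the log Crude OR, with equal pre and post variances and correlation r between the pre and post log ORs:

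- Crude (coefficient 0): V
- Adjusted (coefficient 1): 2(1 − r)V
- Estimated coefficient (best value r): (1 − r²)V
- Adjusted relative to estimated: 2(1 − r)/(1 − r²) = 2/(1 + r), which exceeds 1 for every r below 1

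**Values of r (assumed).** For equal physician volumes and stable preferences, r = m·ICC/[1 + (m − 1)·ICC].

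| m | ICC | r | Adjusted/Crude | Estimated/Crude | Adjusted/Estimated |
|---|---|---|---|---|---|
| 3 | 0.05 | 0.136 | 1.727 | 0.981 | 1.760 |
| 3 | 0.10 | 0.250 | 1.500 | 0.938 | 1.600 |
| 6 | 0.05 | 0.240 | 1.520 | 0.942 | 1.613 |
| 6 | 0.10 | 0.400 | 1.200 | 0.840 | 1.429 |
| 6 | 0.20 | 0.600 | 0.800 | 0.640 | 1.250 |
| 6 | 0.30 | 0.720 | 0.560 | 0.482 | 1.163 |
| 12 | 0.30 | 0.837 | 0.326 | 0.299 | 1.089 |

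If preferences drift between windows (autocorrelation 0.8), r falls and the loss grows. Over all settings with m from 3 to 12, Adjusted/Estimated runs from 1.09 to 1.80.

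Against the Crude OR the sign is not fixed. The Adjusted OR is noisier when r is below 0.5. That point is reached at ICC = 1/(m + 1): 0.25 for m = 3, 0.14 for m = 6 and 0.08 for m = 12.

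**Simulation of a covariate model.** Assumptions: 1,691 physicians per arm, logit-normal physician propensities and episodes pooled as in the plan. The model is a logistic regression on arm and the logit of the shrunken pre-period proportion, with an indicator for no pre-period episodes, standardised to a marginal OR.

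- 24 settings (m = 3, 6, 12; volume CV 0 or 1; ICC 0.05–0.30; 1,000 runs each): Adjusted/covariate variance ratio 1.10 to 1.77. Since √1.10 ≈ 1.05 and √1.77 ≈ 1.33, intervals are about 5% to 33% wider. The Adjusted OR was noisier than the Crude OR in 9 settings and less noisy in 15.
- 16 settings at m = 6, also varying nitrofurantoin share (30–70%) and stability of preference: 1.15 to 1.62, or about 7% to 27% wider.
- m = 6, equal volumes, ICC 0.10: SD of the log OR 0.0332 Crude, 0.0369 Adjusted, 0.0307 covariate-adjusted.
- m = 6, volume CV 1, ICC 0.20: 0.0524, 0.0388 and 0.0331.
- Mean log ORs of the three estimators agreed within about 0.003, so no bias appears.

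**Power illustration** (m = 6, equal volumes, ICC 0.10, 50% nitrofurantoin, true marginal OR 1.09, log 0.0862). Adjusted: 0.0862/0.0369 − 1.96 = 0.38, power about 65%. Covariate: 0.0862/0.0307 − 1.96 = 0.85, power about 80%. The OR detectable with 80% power is exp(2.80 × 0.0369) = 1.11 against exp(2.80 × 0.0307) = 1.09. In closed form at m = 3, V = 2 × 1.2/(1,691 × 3 × 0.25) = 0.00189. The SDs are then √(1.5V) = 0.0533 and √(0.9375V) = 0.0421, and power is about 37% against 53%.

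**The case against.** The strongest reply is that this is a preference for efficiency and not an error. The ratio of ORs is explicitly defined, valid under randomisation and readable from one table. It already captures much of the benefit of the baseline data, beating the Crude OR in 15 of the 24 settings. All of that stands, and it limits the point to an improvement.

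Several narrower objections also have force:

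- The OR of 1.09 is not in the documents; it is the value at which the covariate model reaches 80% power. The ICC, the 50% share and the equal volumes are assumed too. The power figures are one case and nothing more.
- The 6 visits may well be a total over both windows, which suggests about 3 per period. The absolute power figures then fall, but the relative loss rises (variance ratio 1.60 against 1.43 at ICC 0.10).
- The plan does not say how its 95% limits are computed, so the width it would actually report is unknown. The widths above apply to intervals that reflect the true sampling variability. The missing interval method is a separate issue.
- The 2/(1+r) result holds in large samples for an estimated coefficient on the pooled log OR. For the logistic model with unequal volumes the advantage rests on simulation. Further simulations of that model, including one over 96 settings with 1.5 to 6 episodes per period and volume CV up to 3, favoured it in every setting.

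None of these reverses the direction.

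**Conclusion.** The point holds. For A vs B, A vs C and C vs B, fixing the coefficient at 1 is in large samples never more precise than estimating it, and is strictly less precise unless the pre-to-post slope is 1. That direction needs no assumed ICC.

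The size does. Over plausible but assumed volumes, ICCs and stability of preference, the variance penalty runs from about 10% to about 80%. It is smallest where volume and between-physician variation are both high. Confidence in the size is therefore only moderate.

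The loss is precision and not bias when averaged over randomisations. Given a particular chance imbalance at baseline, a coefficient of 1 over-corrects. The argument does not extend to Arm B vs Arm C with a pre-period that follows Arm C's letter.

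**What to change.** For the three early-mailing comparisons, name as the main estimate a post-period logistic model of nitrofurantoin (yes/no) on arm and the physician's nitrofurantoin proportion in the 6 months before 23 September 2021. Use physician-clustered standard errors. Standardise the result to a marginal OR, so that it targets the same quantity as the plan's OR; the unstandardised conditional OR would not.

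State in advance how the baseline proportion is shrunk toward the mean, or that an indicator marks physicians with no pre-period episodes, and over which episodes the result is standardised.

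For Arm B vs Arm C, use only pre-September 2021 prescribing as the covariate, and do not assume equal means just before the March 2022 mailing. Keep the ratio of ORs as a secondary display.

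The cost is SAP wording and a regression in place of a hand formula. No new data are needed: item 2 already takes prescribing "from 6 months prior to first mailing to the end of the delay period", although the model needs it at physician level and not as eight pooled cells. The downsides are less transparency and the need for a rule on physicians without baseline episodes. Section 4 partly describes the trial in the past tense, so the SAP should record whether the change was made before outcomes by arm were seen.
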